11.3.4. Safety Analysis

The safety evaluation will include assessment of AEs, vital signs, clinical laboratory safety tests, and physical examination findings.

For each continuous laboratory parameter, results will be categorized as low, normal, or high based on the laboratory normal ranges, if applicable. Frequencies and percentages will be presented by

gender and BMI group for participants who had a shift to low and for participants who had a shift to high from baseline to any post-dosing assessment, if applicable.

The number and percentage of participants with normal and abnormal physical examination results will be presented for evaluations at baseline, each indicated visit and final visit, if applicable. Individual and summary clinical laboratory data will be presented in tabular form with mean, median, standard deviation, and range (minimum and maximum) as appropriate.

12. Protocol Deviations

Protocol Deviation (PD) forms must be filed for any deviation from this protocol. PDs which place participants at increased risk of harm, or affect data integrity may be considered Protocol Violations (PVs) and must be reported to the appropriate regulatory authorities no later than 2 weeks (10 business days) from the time of identification. PDs will be filed in the applicable participant chart, and in the Trial Master File upon study closeout. PDs will be filed and signed by delegated study staff and reviewed and signed by the PI. The PI will determine if the PD is reportable to the IRB based on an assessment of the participant's safety and/or the effects on the integrity of the study data.

13. Protocol Amendments

Any changes to the protocol must be tracked and documented in the form of an amendment after it has been reviewed by the appropriate regulatory bodies. The reasons for change must be documented in writing and provided to the regulatory bodies and included in the Trial Master File (TMF). These changes will be subject to regulatory approval prior to implementation. All amendments will be documented in the study report.

14. Data Collection and Storage

The PI and/or delegated site staff agree to maintain accurate CRFs and source documentation. Source documents are the originals of any documents which will be used by the site that allow verification of the existence of the participant and substantiate the integrity of the data collected during the trial.

dicentra will supply either paper or electronic CRFs for each participant. CRFs will be completed only by persons delegated by the PI. Corrections will be made so as not to obliterate original data and will be identified and dated by the person who made the correction. The PI will allow designated representatives and regulatory bodies to have direct access to the source documents to verify the data reported in the CRFs.

All study records will be retained by the site for a period of 25 years after study completion.

An independent, third-party clinical trial management system (CTMS) software vendor may be used at the site for laboratory report data and participant-associated document storage. All activities and actions performed on the vendor platform will be tracked and will product an electronic audit-trial in accordance to regulatory standards.

Paper documents will be used in the event that the CTMS system is not used due to any unforeseen or incidental circumstance causing disruption to data collection. All paper documentation will be subject to ICH-GCP E6(R2) and applicable guidelines.

All site-specific documentation generation and management, including documents shared with the Sponsor prior to the start of the study follow internal SOPs for version control and approval for implementation. All procedural SOPs, reports and source documents that will be shared with the Sponsor during and after the study, including those that require changes during the course of the study, will be reviewed and approved by the appropriate site staff in accordance with site approval processes and SOPs.

15. Ethical Considerations

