1. To evaluate the safety of AllerPops administration in volunteers with seasonal/year-long allergies during a 21-day intervention period.
2. To assess the duration of effectiveness of AllerPops in relieving nasal symptoms compared to the control group in volunteers with seasonal/year-long allergies during a 21-day intervention period (exploratory).
3. To evaluate the effect of the AllerPops administration on the oral microbial presentation/microbiota using Amplicon Metagenomics Sequencing test through saliva samples during a 21-day intervention period (exploratory).
4. To evaluate the effect of the AllerPops administration on the IgE (total) blood level during a 21-day intervention period (exploratory).

Study Population: Seventy-two participants with seasonal/year-long nasal allergies.

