For the control group, the same investigational product will be administered, however the procedure for use will be modified as follows: There will be no mouth cleaning before the product consumption (No step 1 as mentioned above). The product will be swallowed instead of dissolved in the mouth, in order to reduce its presence in the mouth as much as possible. The purpose of this control group is to support the effect of use of the entire two-step method as compared to the investigational group.

The active ingredient, L-Arginine is known to Health Canada. L-Arginine is listed in the NHPID, and allowed for use in NHPs under proposed here conditions of use. Safety of the of current ingredient combination, while allowed for use separately, will also be tested under proposed conditions of use.

The Rationale for Performing Research:

Increase in immune-mediated conditions [30]–[32](Allergic rhinitis is one of them) and the few medical solutions available (each of which is associated with side effects) prompted this research and clinical study. The medicinal ingredient, L-Arginine, in the formulation of AllerPops is a well-known Natural Health Product Ingredient with history of human use.

4. Study Objectives

Objectives:

Primary Objective: To assess the effectiveness of AllerPops on relieving nasal symptoms compared to the control group in volunteers with seasonal and perennial (or intermittent and persistent) allergic rhinitis during the first 7 days of the 21-day intervention period.

Secondary Objectives:

1. To evaluate the safety of AllerPops administration in volunteers with seasonal/year-long allergies during a 21-day intervention period.
2. To assess the duration of effectiveness of AllerPops in relieving nasal symptoms compared to the control group in volunteers with seasonal/year-long allergies during a 21-day intervention period (exploratory).

3. To evaluate the effect of the AllerPops administration on the oral microbial presentation/microbiota using Amplicon Metagenomics Sequencing test through saliva samples during a 21-day intervention period (exploratory).
4. To evaluate the effect of the AllerPops administration on the IgE (total) blood level during a 21-day intervention period (exploratory).

Endpoints:

Primary Endpoint: The reduction of nasal allergic symptoms during the first 7 days of the 21-day intervention period (once every other day – D1, D3, D5). The reduction of symptoms will be measured using the following assessments.

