6.6 Blinding and Unblinding

Blinding of study products will be maintained by appropriately delegated study staff. Designated unblinded personnel will randomize the groups using block randomization ensuring an equal distribution in each group. All site staff (excluding designated unblinded personnel) will remain blinded throughout the study until the data-lock and study-closeout stage.

Since both groups will be receiving identical products (with different instructions of use for each group), emergency unblinding will not be applicable to this trial.

7. Study Design (Flow chart)

8. Planned Study Visits

Pre-Screening Telephone Call:

Potential participants who will be contacted to participate in this study will be pre-screened over the phone. They will be asked a series of questions about their health and lifestyle. As part of that telephone pre-screening the following questions will be asked regarding their allergy symptoms:

- 1- How do you score your nasal congestion (0-5, with 5 being the worst)?
- 2- How do you score your Nasal Discharge or sneezing (0-5, with 5 being the worst)?
- 3- How do you score your watery or itchy eyes (0-5, with 5 being the worst)?
- 4- How many times do you brush your teeth a day (0-3, 0,1,2,3 or more)?
- 5- How many times do you use mouthwash a day (0-2, 0,1,2 or more)?
- 6- How many times do you floss your teeth a day (0-2, 0,1,2 or more)?

Scoring Standards: Total score ≥ 7 in question 1-3 and Total score ≤ 4 in question 4-6 will be booked for Screening (V1). Potential participants with a total score of < 7 in question 1-3 and/or total score > 4 in question 4-6 will not pass the telephone pre-screening and will not be booked for Visit 1.

Visit 1 – Screening

Participants will not be required to fast prior to this visit. The delegated study staff will present the ICF, and review its contents with the participant. The study staff will answer any questions the participant may have.

The Informed Consent Form (ICF) will be provided to the participant. After a sufficient period of reflection, the written and informed consent of the participant will be sought. Each page of the ICF will be initialed and the last page will be signed by the participant. Once signed and attested to by the PI or delegate, a copy of the signed original ICF will be provided to the participant.

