11.1. Determination of Sample Size

Seventy-two participants will be participating in the study. The sample size was chosen based on the G*Power calculator in order to detect an effect of 0.6 (Medium effect size) considering 80% power in t tests. Parametric statistical techniques including, but not limited to t tests -

Means: Difference between two independent means (two groups) will be performed on data sets which meet all requirements for normality and variance. The application of non-parametric techniques might be used for relevant data sets. Should any of the statistical methods proposed prove unsuitable during the final analysis, more appropriate methods will be used, and any changes will be documented in the clinical study report, including the rationale for use. These include the transformation of the data (for example to a logarithmic scale) in order to satisfy model assumptions, if applicable. A p-value of < 0.05 will indicate statistical significance for all tests. An exploratory data analysis (EDA) will be performed for the exploratory study part to analyze and investigate data sets and summarize the main characteristics, employing data visualization methods.

[figure not shown]

Figure 1: Analysis: A priori: Compute required sample size.

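### Section 11.3.4 tabulates laboratory shifts by gender and BMI group without naming the randomised arm, so followed literally the tables cannot show a difference between the two methods of use

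*Combined protocol and SAP*

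**What the plan says.** Section 11.3.4 (Safety Analysis) classifies each continuous laboratory result against the laboratory's normal range. It then sets the grouping for the counts and percentages: "gender and BMI group for participants who had a shift to low and for participants who had a shift to high from baseline". All assessments after dosing count, where applicable. Gender and BMI group are the only groupings named in the section. No BMI cut-points are given; the inclusion criteria admit 18.5 to 29.9 kg/m². For adverse events, vital signs, physical examination and laboratory summary statistics, the section names no grouping at all.

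The safety objective in the synopsis and section 4 reads "To evaluate the safety of AllerPops administration in volunteers with seasonal/year-long allergies during a 21-day intervention period". It does not mention the control group. Section 3 (Background) adds: "Safety of the of current ingredient combination, while allowed for use separately, will also be tested under proposed conditions of use".

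Both arms take the same product. Under section 6.4 the investigational arm brushes, scrapes the tongue, gargles hot water and lets the lozenge dissolve. The control arm softens, cuts and swallows it. Section 6.6 allocates participants "using block randomization ensuring an equal distribution in each group".

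**The concern.** The trial randomises the method of use. The one safety table with a stated layout is split by two baseline characteristics and not by the factor that was randomised. Section 6.6 describes block randomisation to equal groups and mentions no stratification. Each gender or BMI row would therefore be expected to hold a mixture of both arms, and an arm difference would not show up indirectly through those rows.

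The method of use could also change exposure. Under section 6.4 the investigational arm discards any lozenge left after 60 minutes, while controls swallow the pieces. After the third dose both arms choose whether to continue, through Day 13. Amounts taken may therefore differ by arm, and a table without arm columns would combine them unseen.

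At stake is whether a reader of the study report can see if laboratory shifts were more frequent under one method than the other.

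**Working it through.** **Step 1. Is a by-arm safety presentation specified elsewhere?**

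- 11.2 (Study Population): analyses participants in their assigned groups. This sets who is analysed and in which group. It does not set a table layout.
- 11.3.2 (Secondary Variables): items 2 to 4 (TNSS and PNIF, microbiota, IgE) are each assessed by comparing the two groups. Item 1, safety, is the only item without that wording.
- 11.3.3 (Data Analysis): describes the primary variables and plans exploratory analysis of the secondary variables, with safety excepted.
- 11.3.4 (Safety Analysis): gender and BMI group for shifts; no grouping for the rest.

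So 11.3.4 is the only specification of safety outputs, and the arm is absent from it.

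**Step 2. Arm size.** Section 11.1 states "Seventy-two participants will be participating in the study", and equal allocation gives 72 / 2 = 36 per arm. The stated design inputs are "detect an effect of 0.6 (Medium effect size) considering 80% power in t tests" and "A p-value of < 0.05 will indicate statistical significance for all tests"; the sidedness is not in the readable text. An exact two-sample t calculation gives:

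- one-sided: 35.04, rounded up to 36 per arm, 72 in total, which reproduces the plan (power 0.809 at 36 per arm);
- two-sided: 44.6, rounded up to 45 per arm, 90 in total, which does not (power 0.709 at 36 per arm).

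The sidedness is a separate matter. Only the 36 per arm is used below.

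**Step 3. What a table without arm columns can show.** Assume 6 participants in total with a shift on some parameter. This count is an illustration, not a figure from the documents. The overall rate is 6/72 = 8.3% in every row.

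| Investigational v control | Rates by arm | Two-sided Fisher p | Overall |
|---|---|---|---|
| 6 v 0 | 16.7% v 0% | 0.025 | 8.3% |
| 5 v 1 | 13.9% v 2.8% | 0.20 | 8.3% |
| 3 v 3 | 8.3% v 8.3% | 1.0 | 8.3% |

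For the first row, p = 2 × C(36,6) / C(72,6) = 2 × 1,947,792 / 156,238,908 = 0.025.

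Splitting the 6 by gender or BMI group does not tell these rows apart, because arm is not one of the splits.

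**Step 4. What a total column adds.** With no events among n participants, the one-sided 95% upper bound on the rate is 1 − 0.05^(1/n). For n = 36 this is 8.0%; for n = 72 it is 4.1%. The combined figure is the more precise one for a question about the product in either mode of use, so it should be shown beside the arm columns.

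**The case against.** The strongest reply is that the safety objective sets no comparison. The primary objective and secondary objective 2 refer to the control group; safety objective 1 does not. Both arms ingest the product, so an overall summary answers the objective as worded. That stands, and it is why the total column belongs in the table. It does not settle the matter, because the microbiota and IgE objectives in section 4 are not worded as comparisons either, yet 11.3.2 compares both between groups.

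Second, the plan omits arm columns but does not forbid them. Section 11.3.4 also promises individual laboratory data, and section 6.5 restricts the randomisation list only until database lock. The tables could be rebuilt by arm, so nothing is lost irretrievably. This also stands. The defect is in what the plan commits to report.

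Third, the documents give no reason to expect cleaning or dissolving to change blood counts, liver enzymes or electrolytes, and no rates. Any numerical example is assumed.

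A reader might infer three stronger points that the documents do not support:

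- *Arm columns would separate product-related shifts from background.* They would not. Controls take the same product, so a product effect could appear in both arms, and equal rates would not show that the product has none.
- *Only the investigational arm meets the safety aim in section 3.* The phrase about conditions of use is not defined there as the two-step method. Its sentence concerns the ingredient combination, which both arms ingest.
- *The combined rate understates the investigational rate by half.* That follows only if control is assumed to have no events, as in the 6 v 0 row.

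**Conclusion.** The point holds as a gap in presentation. For the laboratory shift tables the plan states a grouping, and that grouping leaves out the randomised factor. For adverse events, vital signs, physical examination and laboratory summaries it is only silent, which is a weaker fault. Sections 11.2, 11.3.2 and 11.3.3 do not fill the gap.

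Its practical size cannot be estimated from the documents. The illustration shows only that splits ranging from p = 0.025 to p = 1.0 give the same 8.3% overall. The conclusion assumes that 11.3.4 would be programmed as written and that the two methods of use are of interest for safety as well as efficacy. It does not imply that a safety signal is expected, that safety data would be lost, or that the trial can test product against no product.

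**What to change.** Amend 11.3.4 along these lines:

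> Laboratory shift tables will be presented by randomised arm as assigned, with a total column. Gender and BMI group (cut-points to be stated) will be a supplementary breakdown within arm. Adverse events, vital signs, physical examination findings and laboratory summaries will use the same arm and total columns. The contrast between arms reflects the method of use, since both arms take the same product. The total column addresses the safety objective, which is not comparative.

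Tabulating as assigned agrees with 11.2, which keeps participants in their randomised group regardless of what they received. Within-arm counts by gender and BMI group will be small, so that breakdown should stay descriptive.

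The cost is a few sentences and a different column layout. It needs no extra data, visits or participants.

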15.1. IRB Approval

All necessary forms, advertisements, and subject-facing study documents will be compiled into a submission to an Institutional Review Board (IRB) for approval prior to the conduct of the study. No conduct of the trial will commence until written approval has been obtained from the IRB. dicentra must adhere to the requirements of the IRB and notify them of any study document changes, protocol amendments, and reportable protocol deviations/violations. Study termination must be reported to the IRB, and renewal of study approval must be obtained annually (or as per IRB's stipulations).

15.2. Informed Consent Form

Informed consent will be obtained from participants by delegated study staff. The staff will explain the study and review each page of the consent document. Participants will then be asked to review the consent document, initial each page, and sign the appropriate section(s). The Informed Consent Form (ICF) will contain pertinent study details, a statement indicating the participant is free to withdraw from the study at any point and for any reason, contact information of the IRB (to report ethical concerns), local and applicable regulations surrounding disclosure of personal and health information of the participants, compensation information, and a section explaining the potential risk(s) of participating in the study.

15.3. Risks and Procedures to Minimize Risk

Potential risks are disclosed to the study participants in the ICF prior to their participation in the study. The potential risks associated with the study include venipuncture and associated risks. The risks of venipuncture (at the site) include:

- Pain
- Bruising
- Infection

All venipuncture will be performed by certified phlebotomists and all applicable procedures will be carried out to minimize risk of infection.

The major active ingredient in the product, L-Arginine (402.81mg per dosage unit), does not affect endocrine, hepatic or renal function and can be safely used in adults. However, the individual with or at risk of cancer are excluded due to possible increased risk of adverse event occurrence.

The potential risks associated with the study product include development of low-grade fever, feeling tiredness or low-energy, and mild headache. Emergence of adverse events will be assessed at each visit.

16. Quality Assurance and Quality Control

16.1. Auditing

All material used in this clinical trial will be subject to quality control. This study will be conducted in accordance with ICH-GCP E6(R2) and all applicable Regulations and local laws. Quality assurance audits may be performed by the Sponsor or any health authority during the course of the study or after its completion.

The PI and site agree to comply with the Sponsor and regulatory requirements for auditing the study. This includes access to the source documents for source data verification.

16.2. Monitoring

Prior to the start of the study, the Sponsor representatives, site personnel, and any third-party vendor representatives will hold at least one meeting to go over the details of the study design and plans for study execution. During the study, the Sponsor may arrange the visit of appointed site monitors to ensure that the execution of the study plan by the site meets the Sponsor's expectations and follows the study protocol objective. The site's delegated staff will monitor the conduct of the study and documentation throughout the course of the trial.

16.3. Data Management

16.3.1. Source Data and Source Documents

As defined by the International Conference on Harmonization (ICH), source data are defined as all information in original records and certified copies of original records of clinical findings, observations, or other activities in a clinical study necessary for the reconstruction and evaluation of the study.

All source data and source documents will be stored and archived according to local regulatory requirements. For this study, source data and documents include, but are not limited to:

- Signed and dated Informed Consent Form (ICF);
- Name, gender, date of birth and other personal information/demographic information;
- Participant ID;
- Date and time of each visit;

- All clinical measurements and laboratory results;
- Status of participant throughout the study;
- Paper-based or electronic daily diary (to record any concomitant medications, pre-emergent adverse events, changes in health, dosing time, and adverse events);
- Reason for discontinuation/withdrawal, if applicable.

